ί Π			
Name of company:			Boehringer
Boehringer Ingelheim			Ingelheim
Name of product: Spic	olto		
Name of sativa ingradi		-	
Tiotronium bromide -	± Oladateral		
	r Olodalei ol		
Protocol date:	Study number:	Version/Revision:	Version/Revision date:
12 December 2019	1237-0094	1.0	NA
© 2019 Boehringer Ing This document may not -	Proprietary elheim International GmbF in full or in part - be passed on,	confidential information I or one or more of its affiliated compreproduced, published or otherwise used wit	oanies. All rights reserved. hout prior written permission
Rationale and background:	 International GmbH or one or more of its affiliated companies. All rights reserved. n full or in part - be passed on, reproduced, published or otherwise used without prior written permission The treatment of COPD involves multiple therapies, including long-acting β2 agonists (LABA) (with and without inhaled corticosteroids (ICS) and long-acting muscarinic antagonists (LAMA), with combinations of these drugs now formulated into single inhalers. There are recommendations to restrict triple therapy use further, to only patients who are likely to respond to ICS (such as those with asthma-COPD overlap or patients with high risk of exacerbations and elevated blood eosinophils [P15-08642, P07-11503, R19-3048]. There is an increasing body of evidence suggesting that ICS are particularly effective at reducing the incidence of COPD exacerbations in patients only with a very high blood eosinophil concentration, but not in normal levels [P18-09975]. Hence there is a clear need for better evidence on specific patient populations upon which to base treatment recommendations. This non-interventional study aims to assess the comparative effectiveness of combination LAMA/LABA and ICS (fixed or open), and to explore whether this varies across COPD sub populations defined by exacerbation risk. The 		

c30699487-01

Name of company:			Boehringer
Boehringer Ingelheim			Ingelheim
Name of product: Spiol	to		-
Name of active ingredie	ent:		
Tiotropium bromide +	Olodaterol		
Protocol date:	Study number:	Version/Revision:	Version/Revision date:
12 December 2019	1237-0094	1.0	NA
© 2019 Boehringer Inge This document may not - in	Proprietary Iheim International GmbH n full or in part - be passed on, 1	confidential information I or one or more of its affiliated comp reproduced, published or otherwise used with	panies. All rights reserved. hout prior written permission
objectives:	with Tio+Olo in comparison to patients treated with ICS/LABA/LAMA. All analyses will be repeated in sub-groups of patients under high- or low risk of exacerbation based on (1) previous history of exacerbations in the year preceding cohort entry (with exacerbation history defined as either 1+ hospitalization or 2+ exacerbations in emergency department or outpatients settings [R05-1384]), and (2) circulating eosinophils (cut-off B-Eos 300 cells/uL [P18-09975]) Both overall and among those without a history of exacerbation. The primary objective is to compare the effectiveness of maintenance therapy initiation with the combination treatment Tiotropium and Olodaterol (Tio+Olo) compared with any LABA/LAMA/ICS combination in COPD as		
	The secondary objecti therapy initiation with LABA/LAMA/ICS co pneumonia. Additionally, we will a LABA/LAMA/ICS in cost overall and by car	ve is to assess the association be the combination treatment (Tio ombination in COPD and time to assess differences between Tio+ healthcare utilization and all-ca re setting.	etween maintenance +Olo vs any community acquired Olo vs any use and COPD-specific
Study design:	A incident new-user c via fine stratification	cohort design will be used, with and reweighting of time-condition	confounding controlled onal propensity scores

c30699487-01

IT			1
Name of company:			Boehringer
Boehringer Ingelheim			Ingelheim
Name of product: Spiol	to		_
Name of active ingredie	nt:		
Tiotropium bromide +	Olodaterol		
	1		
Protocol date:	Study number:	Version/Revision:	Version/Revision date:
12 December 2019	1237-0094	1.0	NA
© 2019 Boehringer Ingel This document may not - ir	Proprietary heim International GmbH n full or in part - be passed on, 1	confidential information I or one or more of its affiliated compreproduced, published or otherwise used wit	oanies. All rights reserved. hout prior written permission
Population:	The cohort will consist of all patients in the HIRD with a diagnosis of COPD who received Tio+Olo or combination LABA/LAMA/ICS treatment from 1 January 2013 until 31 March 2019 (or the most recent date available at the time of cohort extraction). To increase the likelihood of a diagnosis of COPD and decrease the likelihood of including misdiagnosed asthma patients, we will only include patients 40 years of age or older on the index date and exclude all patients with a diagnosis of asthma within the year prior to the index date or lung cancer, interstitial lung disease, or lung transplantation at any time prior to the index date. Patients will have at least one year of medical history information prior to the cohort entry date to allow the identification of new use and the measurement of baseline covariates. Patients will be followed until switching to the other treatment, other changes in therapy, discontinuation of COPD treatment, the end of the individual's health plan eligibility, or the end of the study period, whichever occurs first. Main analyses will be limited to the first year following the index date.		
Study data source:	showing eosinophil levels will occur for relevant sensitivity analyses.		
			رب ال
Expected study size:	Overall:		
	New users of Tio+Old	p: 5,458	
	New users of LABA/I	LAMA/ICS: 42,361	
	With eosinophil result	t data:	
	New users of Tio+Old	p: 2,198	
	New users of LABA/I	LAMA/ICS: 15,712	
Main criteria for inclusion:	- New users of Tio+O either as a fixed-dose (LABA/ICS + LAMA March 2019.	lo on the same date or of LABA combination (LABA/LAMA/IC , etc), on the same date between	, LAMA and ICS, S) or free combination a January 2013 and
	index date	prior to first maintenance inhale	$r and age \ge 40$ years at

data.

SI Study Number 1237-0094 c30699487			c30699487-01
Proprietary confidential inf	formation © 2019 Boehringer II	ngelheim International GmbH or one or mor	e of its affiliated companies
Name of company:			Boehringer
Boehringer Ingelheim			Ingelheim الا
Name of product: Spiol	to		
Name of active ingredie	nt:		
Tiotropium bromide +	Olodaterol		
Protocol date:	Study number:	Version/Revision:	Version/Revision date:
12 December 2019	1237-0094	1.0	NA

1. LIST OF ABBREVIATIONS AND TERMS

AE	Adverse Event
BI	Boehringer Ingelheim
BMI	Body Mass Index
CI	Confidence Interval
COPD	Chronic obstructive pulmonary disease
CPRD	Clinical Practice Research Datalink
DSAs	Data Sharing Agreements
ED	Emergency Department
EMA	European Medicines Agency
FDC	Fixed Dose Combination
GVP	Guideline on Good Pharmacovigilance Practices
HIPAA	Health Insurance Portability and Accountability Act
HIRD	HealthCore Integrated Research Database
ICD-10	International Classification of Disease, Version 10
ICS	Inhaled corticosteroids
IR	Incidence Rate
IRB	Institutional Review Board
ITT	Intention to treat
LABA	Long-acting beta2-agonist
LAMA	Long-acting muscarinic antagonists
Ν	Number
PHI	Protected Health Information
PS	Propensity score
PSTAT	Project Statistician
PY	Person-years at risk
RR	Rate Ratio
TIO+OLO	Tiotropium+Olodaterol

TM Epi	Team Member Epidemiology
cells/µL	Microliter
US	United States
UTS	Up-to-standard

Proprietary confidential information © 2019 Boehringer Ingelheim International GmbH or one or more of its affiliated companies

2. **RESPONSIBLE PARTIES**

(Principal Investigator)

Tel:

3. AMENDMENTS AND UPDATES

There are currently no amendments to the protocol.

4. MILESTONES

Milestone	Planned date
Start of data collection:	August 1, 2019
Data extraction and coding	
End of data collection:	Not applicable. This study is an observational study based on
	existing data.
Study progress report(s) as	Not applicable
referred in Article	
107 m(5) of Directive	
2001/83/EC:	
Interim report(s) of study	Not applicable
results:	
Registration in the EU PAS	Not applicable
register	
Final report of study	April 2020 (Preliminary results: 19 December 2019)
results:	

Proprietary confidential information © 2019 Boehringer Ingelheim International GmbH or one or more of its affiliated companies

5. **RATIONALE AND BACKGROUND**

The treatment of COPD involves multiple therapies, including Long-acting $\beta 2$ agonists (LABA) (with and without inhaled corticosteroids (ICS) and long-acting muscarinic antagonists (LAMA), with combinations of these drugs now formulated into single inhalers.

Several trials compared a single-inhaler triple therapy with an ICS/LABA and a LAMA respectively and found greater benefit with triple FDC [P19-08111]. However, they represent a limited view of the patients who could potentially use these treatments so that a real-world study of patients who are representative of clinical practice is of interest.

There are recommendations to restrict triple therapy use further, to only patients who are likely to respond to ICS (such as those with asthma-COPD overlap or elevated blood eosinophils [P15-08642). There is an increasing body of evidence suggesting that ICS are particularly effective at reducing the incidence of COPD exacerbations in patients only with a very high blood eosinophil concentration, but not in normal levels [P18-09975]. Hence there is a clear need for better evidence on specific patient populations upon which to base treatment recommendations.

This non-interventional study aims to assess the comparative effectiveness of combination Tiotropium and Olodaterol (Tio+Olo) (FDC) compared to combination LAMA/LABA and ICS (fixed or open) This study will provide useful data on the relative benefits of different combinations in treating COPD patients The intended audiences are payers and prescribers. The results from the study will be published in the scientific literature.

Proprietary confidential information © 2019 Boehringer Ingelheim International GmbH or one or more of its affiliated companies

6. **RESEARCH QUESTIONS AND OBJECTIVES**

The goal of this study is to investigate the risk of COPD exacerbations, community acquired pneumonia, and health care utilization in patients treated with Tio+Olo in comparison to patients treated with ICS/LABA/LAMA. All analyses will be conducted for the total population, as well as in sub-groups of patients under (1) high- or low risk of exacerbation based on previous history of exacerbations in the year preceding cohort entry (cut-off: 0-1 vs 2+ exacerbations [P07-11503], (2) circulating eosinophils (cut-off B-Eos 300 cells/uL, [P18-09975]), and (3) as an exploratory analysis, a combination of exacerbation history and circulating eosinophils.

Primary objectives:

The primary objective is to compare the effectiveness of new use of maintenance therapy initiation with the combination treatment Tiotropium and Olodaterol (Tio+Olo) compared with new use of LABA/LAMA/ICS combination in COPD as the time to the first COPD exacerbation.

Secondary objective:

The secondary objective is to assess the association between maintenance therapy initiation with the combination treatment (Tio+Olo vs any LABA/LAMA/ICS combination in COPD and time to community acquired pneumonia.

Exploratory objective:

To assess differences between Tio+Olo vs any LABA/LAMA/ICS in all-cause and COPD-specific healthcare utilization and cost overall and by care setting.

Proprietary confidential information © 2019 Boehringer Ingelheim International GmbH or one or more of its affiliated companies

7. **RESEARCH METHODS**

7.1 STUDY DESIGN

Population-based incident new-user cohort design.

7.2 SETTING

The study will be conducted using administrative healthcare claims and laboratory result data captured in the HealthCore Integrated Research Database (HIRD; details in Section 7.5). The observation period will be from January 2013 until the most recent date available at the time that the cohort is extracted (estimated March 2019).

7.3 SUBJECTS

The study cohort will be formed based on the following entry criteria.

Inclusion Criteria:

- 1. At least one prescription for Tio+Olo or a LABA/LAMA/ICS combination between 1 January 2013 and 31 March 2019.
 - a. For Tio+Olo users, the first dispensing of Tio+Olo will be defined as the index date.
 - b. LABA/LAMA/ICS use can occur either in free or fixed combinations. The first date when all three medications are used based on either concurrent or overlapping dispensings in the pharmacy claims data will be defined as the index date.
- 2. At least one diagnosis of COPD at any time prior to the index date.
- 3. At least one year of continuous medical and pharmacy health plan eligibility prior to the index date will be required to allow a baseline period for the covariates and identification of new use of the study drugs.

Exclusion Criteria:

- 1. To increase the likelihood of a true diagnosis of COPD, we will exclude:
 - a. All patients less than 40 years of age on the index date, and
 - b. All patients with a diagnosis of asthma in the year prior to the index date
- 2. To limit the population to those without severe lung compromise outside of COPD, we will exclude individuals with lung cancer, interstitial lung disease, or lung transplant identified at any time prior to the index date
- 3. To restrict the cohort to new users of Tio+Olo or LABA/ICS, we will exclude any individual with use of either Tio+Olo, LABA/ICS, or LABA/LAMA/ICS combination therapy in free or fixed form for at least one year prior to the index date.

Outpatient laboratory data is available for a subset of patients. Some analyses will be further restricted to the subset of the population with at least one laboratory result showing circulating eosinophil levels within six months before the index date.

Individuals in the study cohort will be followed from the index date until the earliest of the date of a switch in treatment, addition of ICS for the Tio+Olo group, discontinuation of

COPD treatment, the end of the study period, or the end of continuous health plan eligibility. Main analyses will be further limited to the first year after cohort entry, with sensitivity analyses considering all available data.

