7.4 VARIABLES

7.4.1 **Exposures**

The exposure measures are based on pharmacy dispensings of the study medications, namely Tio+Olo and LABA/LAMA/ICS combination therapy. As described in the data analysis section, the as-treated analysis, which is the main analysis, will consider continuing exposure of the initial treatment of Tio+Olo or LABA/LAMA/ICS within the treated groups defined by the days supply recorded at the time of pharmacy dispensing, allowing for a gap between dispensings of up to 15 days. This gap is allowed in consideration of plausible delays in obtaining medication refills and continued use beyond the days supplied where medication has been missed due to imperfect adherence, and will be varied in sensitivity analyses (see Section 7.9.2). Codes used to identify study medications are included in Annex 3.1.

The treatment segment ends at the earliest of the following events:

- 1. Fifteen days after the end of the observed days supply for the medication received on the index date without a subsequent dispensing of COPD medication (i.e., discontinuation)
- 2. Initiation of triple therapy (i.e., addition of ICS to Tio+Olo or a LAMA to LABA/ICS (i.e., treatment escalation, applies to Tio+Olo only)
- 3. Any other change in use of study medication by active ingredient, inclusive of a change to a different combination therapy, change from a fixed form to a free form combination therapy, or a change from combination therapy to monotherapy (i.e., switch)

Changes in dose for medications started on the index date will not impact the end of the treatment segment. Codes used to identify study medications are included in Annex 3.1.

7.4.2 **Outcome(s)**

7.4.2.1 **Primary outcome(S)**

The primary outcome event for effectiveness is the first COPD exacerbation to occur after cohort entry. The event is defined as follows:

- Severe exacerbation: •
 - Hospitalization with a principal discharge diagnosis of COPD.
 - Moderate exacerbation:
 - An ED visit with a discharge diagnosis of COPD and/or
 - Dispensing of an antibiotic and an oral corticosteroid on the same day

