7.4.3 Covariates

Patient characteristics at baseline will be assessed for Tio+Olo and LABA/LAMA/ICS user overall and stratified by history of exacerbation, circulating eosinophils, subgroups defined by both exacerbation and eosinophil levels.

We will identify and describe the following demographic characteristics as of the index date:

- Sex
- Age (years, as both a categorical and a continuous variable)
- Calendar year of cohort entry

Proprietary confidential information © 2019 Boehringer Ingelheim International GmbH or one or more of its affiliated companies

- Season of index date (winter, spring, summer, fall)
- US census region of residence
- Insurance type (e.g., Commercial, Medicare)

Additional characteristics will be defined during the 12-month pre-index baseline period:

- Number of previous COPD treatments
- Specific previous COPD treatments
 - LAMA monotherapy
 - LABA monotherapy
 - ICS monotherapy
 - LAMA/ICS combination therapy
 - LABA/ICS combination therapy
- Previous acute COPD exacerbation (measured both overall and in the 30 days prior to cohort entry), categorized as 0, 1, or 2+.
 - All exacerbations (Moderate+Severe)
 - ED visits or dispensings of inhaled corticosteroids/antibiotics (Moderate)
 - Hospitalizations (Severe)
- Use of other respiratory drugs in the 12-month pre-index period:
 - Short-acting beta-agonists
 - Anticholinergics
 - Methylxanthines
 - Muscarinic antagonists
 - Short-acting muscarinic antagonists
- Use of antibiotics for a respiratory condition (e.g., azithromycin)

Chronic comorbidities will be defined using diagnoses identified during all available data prior to the index date, and will include:

- Cardiovascular disease
- Charlson comorbidity index
- Diabetes
- Thyroid disease
- Renal failure
- Autoimmune disease
- Pneumonia
- Obesity*
- Alcohol use disorder*
- Tobacco use or cessation counselling*
- Cancer (excluding basal cell carcinoma)
- * We anticipate limited capture of lifestyle variables known to be risk factors and potential confounders, including obesity, smoking status and excessive alcohol consumption. Although we will describe them as identified in the HIRD, bias analyses to examine the extent to which residual confounding may impact results are also planned.

Additionally to the covariates defined above, we will use the high-dimensional approach to identify variables entering a time-conditional propensity score.

Boehringer Ingelheim	

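### Section 7.3 does not make the two arms mutually exclusive: a patient who starts Tio+Olo with an ICS dispensed or still on hand meets both index definitions on the same date

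*Combined protocol and SAP*

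**What the plan says.** Section 7.3, inclusion criterion 1, gives each arm its own index date. Rule 1a: "For Tio+Olo users, the first dispensing of Tio+Olo will be defined as the index date". Rule 1b sets the triple index date at "The first date when all three medications are used based on either concurrent or overlapping dispensings in the pharmacy claims data", after stating that "LABA/LAMA/ICS use can occur either in free or fixed combinations". Exclusion 3 then says "we will exclude any individual with use of either Tio+Olo, LABA/ICS, or LABA/LAMA/ICS combination therapy in free or fixed form" in at least the year before index.

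Section 7.4.3 lists "ICS monotherapy" and "LAMA/ICS combination therapy" among the previous COPD treatments to be described at baseline.

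Section 7.4.1 ends a treatment segment at discontinuation, at escalation, or at any other change in study medication. The escalation rule reads "Initiation of triple therapy (i.e., addition of ICS to Tio+Olo or a LAMA to LABA/ICS (i.e., treatment escalation, applies to Tio+Olo only". Section 7.3 likewise stops Tio+Olo follow-up when an ICS is added.

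Annex 3.1 lists olodaterol/tiotropium as a LABA/LAMA and single-agent ICS separately. The abstract describes the triple components as started on one date and does not mention overlapping supply.

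**The concern.** The primary contrast is treatment with an ICS against treatment without one. Tio+Olo plus a separate ICS inhaler is a free LABA/LAMA/ICS combination, and Section 7.4.1 treats it as triple therapy when the ICS is added later. When the ICS is there on day 0, the text does not say which arm the patient belongs to.

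Two programmers could therefore build different primary cohorts from the same protocol. One could put these patients in the Tio+Olo arm, so that comparator-treated time counts as Tio+Olo. Another could put them in the triple arm, including patients who were replacing the ICS and had only a few days of supply left. A third could enter them in both. Propensity-score weighting balances covariates between arms as assigned; it cannot repair an assignment that is undefined.

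**Working it through.** **1. Does one patient meet both rules on one date?** Take a patient whose first Tio+Olo dispensing falls on day 0.

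| ICS status on day 0 | Rule 1a (Tio+Olo) | Rule 1b (triple), Section 7.3 | Triple under the abstract's same-date wording |
|---|---|---|---|
| None | met | not met | not met |
| Dispensed the same day | met | met | met |
| Earlier fill, supply still on hand | met | met | not met |

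In the last row the abstract would leave the patient in Tio+Olo only, with the covered time still triple-treated. The abstract and Section 7.3 therefore disagree on that row.

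**2. Does another rule resolve it?**
- Exclusion 3 concerns use before the index date and names Tio+Olo, LABA/ICS and triple therapy. It does not name ICS alone or LAMA/ICS, which Section 7.4.3 expects in the cohort, and it does not address an ICS filled on day 0.
- Escalation (Section 7.4.1, rule 2) and the Section 7.3 stopping rule depend on an ICS being added. ICS already present is not clearly an addition.
- Rule 3 needs a change in study medication. ICS continuing from day 0 is not a change.
- Section 7.9.1 excludes patients who stopped a drug before index. That does not settle cases where supply still covers the index date. Its definition of current use by overlapping days' supply gives no order of precedence between arms.
- Section 7.7 has no row for patients meeting both definitions.

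**3. Illustration of size.** The only effect size in the plan is the hazard ratio of 0.85 in Section 7.7, quoted with over 90% power at 2,000 patients per cohort. That power cannot be reproduced, because no event rate is given. At two-sided 5% (assumed) and 1:1 allocation, 90% power needs 1,592 events, or 1,592/4,000 = 39.8% of patients. The point does not depend on this figure.

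Let f be the share of Tio+Olo person-time that is really triple-treated (assumed), with constant hazards and misplaced patients otherwise exchangeable. Set the true Tio+Olo hazard to 1 and the triple hazard to 0.85. Then

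observed HR = 0.85 / [(1 − f) + 0.85f]

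- f = 10%: 0.85/(0.90 + 0.085) = 0.85/0.985 = 0.863
- f = 20%: 0.85/(0.80 + 0.17) = 0.85/0.97 = 0.876

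On the log scale, ln 0.85 = −0.1625, ln 0.863 = −0.1474 and ln 0.876 = −0.1321, so about 9% and 19% of the log hazard ratio is lost. With events held at 1,592, power falls from 90% to 84% and 75%.

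**4. The reverse error.** If 20% of the 5,469 Tio+Olo starters in Section 7.7 (about 1,094) were wrongly put in the triple arm of 42,227, they would form 1,094/(42,227 + 1,094) = 2.5% of it. The hazard ratio would move from 0.85 to about 0.85 + 0.025 × 0.15 = 0.854. Because the triple arm is so much larger, contamination of the Tio+Olo arm matters more.

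**The case against.** The strongest reply is that the intent is visible. Section 7.4.1 treats ICS with Tio+Olo as triple therapy, Tio+Olo follow-up stops when an ICS is added, and Section 7.9.1 treats exposure as time-dependent. A programmer would probably class a same-day Tio+Olo and ICS fill as triple. That is a fair guess at intent, but no section writes it as an assignment rule, and Section 7.4.1 follows the initial treatment, which is exactly what is undefined here.

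Three stronger readings are tempting, and the documents do not support them.
- A reader might infer that nothing ends these patients' Tio+Olo segments. Discontinuation, switch, loss of eligibility and study end all still apply, and a later ICS fill might be read as an addition. Leftover supply also runs out, so the lasting problem is same-day fills and leftover ICS that is refilled without being treated as an addition.
- A reader might infer that the bias must be toward 1. That needs misplaced patients to be exchangeable with the rest. Section 7.6 itself raises confounding by indication, and patients carrying an ICS may differ in baseline risk, so the net bias could go either way.
- A reader might take 10% to 20% as an estimate, or 0.85 as the expected effect. The shares have no source in the documents, and the 0.85 comes from a CPRD analysis whose treatments Section 7.7 does not name.

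Conversely, the two separate columns in Section 7.7 do not show that the arms are exclusive, because no overlap was counted.

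**Conclusion.** The point stands as a gap in the definition of the primary exposure. A patient with an ICS dispensed or on hand at the first Tio+Olo dispensing satisfies both index rules on the same date, and no other rule settles the arm. This is more than missing detail: followed literally, the rules allow comparator-treated time in the Tio+Olo arm, or the same person in both arms.

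The size is unknown. The shifts to 0.863 and 0.876 rest on an assumed true hazard ratio of 0.85, assumed shares of 10% and 20%, constant hazards and exchangeability. The same definitions carry over to the pneumonia analysis. The rule should be settled before the cohort is built.

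**What to change.** Amend Section 7.3 as follows.

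(a) Rule 1a: admit a patient to the Tio+Olo arm only if no ICS in any form is dispensed on the index date and no ICS days' supply covers it.

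(b) Assign Tio+Olo and an ICS dispensed on the same day to the triple arm only.

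(c) Reconcile the abstract's same-date wording with the overlap wording in rule 1b. Choose one rule for patients whose only ICS coverage at index is leftover supply: either it counts as triple therapy, or such patients are left out of both arms. Apply it to every LABA/LAMA starter in Annex 3.1. Dropping them only among Tio+Olo starters would make selection differ by arm, because an ICS user starting another LABA/LAMA would still enter the triple arm. Do not use refills after index to assign arms. Run the alternative handling as a sensitivity analysis.

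(d) Report in the attrition table how many patients meet both definitions, split by same-day fill and leftover supply.

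The cost is a small amount of programming on days' supply already in the data, and the loss or reassignment of patients with ICS coverage at index. How many that is cannot be told from the documents; item (d) will show it.

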7.5 DATA SOURCES

This study will be conducted using the HIRD, a large administrative healthcare database maintained by HealthCore for use in health outcomes and pharmacoepidemiologic research. The HIRD includes longitudinal medical and pharmacy claims data from health plan members across the United States (US). Member enrolment, medical care (professional and facility claims), outpatient prescription drug use, outpatient laboratory test result data, and health care utilization may be tracked for health plan members in the database dating back to January 2006, and with diagnoses recorded in International Classification of Disease, Version 10 (ICD-10) since October, 2015. Laboratory result data are additionally available for those tests that have been performed using two large, national reference laboratories (Quest and LabCorp) [R14-4278]. The database has been used for the study of numerous diseases, including studies of COPD [R19-2324; R19-2321; R19-2323; R19-2322; P15-11025; P14-12233]

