ANNEX 3.3: DEFINITIONS OF STUDY COVARIATES

Complete list of ICD-9-CM, ICD-10, CPT, HCPCS, and GPI codes.

Medication	HCPCS	GPI
Short-acting beta- agonists		
Levalbuterol	J7617,J7607,J7612,	4420104510X
	J7614,J7615	4420104550X
Albuterol	J7602, J7603,	4420101000X
	J7609-J7611,	4420101010X
	J7613, J7616,	
	17625 04093	
	Q4094	
Terbutaline	J3105,J7680,J7681	442010602X
Isoproterenol	J7657	44201040X
	J7658	
	J7659	
	J7660	
Methylxanthines		
Aminophylline		4430001000x
		4430001010x
Theophylline (SR)	J2810	4430004000x 499100240X
		4499100220X
		4499100242X 4499100250X
		44992203A 44002003X 44002204X 44000003X
		44995005A 44995204A 44999005A 44000602X 4400220310X
		4499960270X
		4499220315X

Boehringer Ingelheim		
Protocol for non-interventional	studies based of	n existing data
BI Study Number 1237-0094		

Medication	HCPCS	GPI
SAMA (Short-acting muscarinic antagonists)		
Ipratropium bromide	J7644, J7655	4230X 44100030X
Antibiotics for a respiratory condition		
Aamikacin	J0278	07000010x
Amoxicillin/potassium clavulanate		0199000220x
Amoxicillin		01200010x
Ampicillin	J0290	01200020x
Ampicillin-sulbactam	J0295	0199000225x
Azithromycin	J0456	03400010x
Aztreonam	S0073	16000005x
Cefaclor		02200040x
Cefdinir		02300040x
Cefepime	J0692	02400040x
Cefixime		02300060x
Cefotaxime	J0698	02300075x
Cefpodoxime		02300065x
Cefprozil		02200062x
Ceftazidime	J0713, J0714	02300080x
Ceftriaxone	J0696	02300090x
Cefuroxime	J0697	02200065x
Ciprofloxacin	J0744	05000020x
Clarithromycin		03500010x
Doxycycline		04000020x
Ertapenem	J1335	16150030x
Erythromycin	J1364	0310x
Gemifloxacin		05000083x
Imipenem	J0743	16159902x
Levofloxacin	J1956	05000034x
Linezolid	J2020	16230040x

 Study Number 1237-0094
 c30699487-01

 Proprietary confidential information © 2019 Boehringer Ingelheim International GmbH or one or more of its affiliated companies

Medication	HCPCS	GPI
Meropenem	J2185	16150050x
Moxifloxacin	J2280	05000037x
Penicillin G benzathine	J0561, J0558	01990002x, 01100020x
Penicillin VK		01100040x
Piperacillin	S0081	01400040x
Piperacillin-tazobactam	J2543	019900027x
Procaine penicillin	J0558, J2510	
Ticarcillin		01400050x
Ticarcillin-clavulanate	S0040	019900023x
Trimethoprim- sulfamethoxazole	S0039	169900023x
Vancomycin	J3370	16000060102x

Condition	ICD9	ICD10	ICD9	ICD10 proc	HCPC	CPT
			proc		S	
Asthma	493	J45				
	493	J45.2				
	493	J45.20				
	493.01	J45.21				
	493.02	J45.22				
	493.1	J45.3				
	493.1	J45.30				
	493.11	J45.31				
	493.12	J45.32				
	493.2	J45.4				
	493.2	J45.40				

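### The Annex 3.3 code lists do not carry out exclusion criterion 2: most adult interstitial lung disease is uncoded, and right- and left-side lung cancer codes are missing

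*Combined protocol and SAP*

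**What the plan says.** Section 7.3 gives the purpose of criterion 2 as "To limit the population to those without severe lung compromise outside of COPD", and then states that "we will exclude individuals with lung cancer, interstitial lung disease, or lung transplant identified at any time prior to the index date". It sets no limit by subtype of interstitial lung disease (ILD) or by side of the tumour, and the abstract repeats the exclusion in the same unrestricted terms. Criterion 1 of the same section restricts the cohort to patients aged 40 or older.

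The conditions are turned into codes in Annex 3.3, whose opening line reads "Complete list of ICD-9-CM, ICD-10, CPT, HCPCS, and GPI codes". The two relevant rows are:

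- **ILD:** ICD-9 516.34 and 516.6*; ICD-10 J84.115, J84.83, J84.841, J84.842, J84.843 and J84.848.
- **Lung cancer:** ICD-9 162, 231.2, 197.0, 176.4, 235.7 and V10.11; ICD-10 C33, C34.00, C34.10, C34.2, C34.30, C34.80, C34.90, C46.50, C78.00, D02.20, D38.1 and Z85.118.

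No broader list for either condition appears elsewhere in the protocol. Section 7.5 says diagnoses are recorded in "International Classification of Disease, Version 10 (ICD-10) since October, 2015".

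**The concern.** The text of the criterion is broad and the codes are narrow. The extraction will follow the codes, so the study report would describe a population that the program did not create.

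This affects the outcomes. As listed in section 7.4.2.1, a moderate exacerbation can be an antibiotic and an oral corticosteroid dispensed on the same day, with no diagnosis attached. A patient treated for ILD or lung cancer can meet that definition without a COPD exacerbation. The secondary outcome is hospitalisation for pneumonia, which such patients can also reach. Section 7.4.2.1 itself treats loss of outcome specificity as the more important threat to validity.

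ILD is the more serious half. It is not among the named covariates in section 7.4.3, so it would be adjusted for only if the high-dimensional procedure happened to select ILD codes.

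**Working it through.** There is no planned figure to reproduce here. The check compares the annex rows with the code families they are meant to represent. The annex prints no descriptors, so code meanings are taken from the standard ICD-9-CM and ICD-10-CM classifications that the protocol adopts.

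**ILD**

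| Codes in the annex row | Meaning in the classification |
|---|---|
| 516.34, J84.115 | respiratory bronchiolitis ILD, one adult subtype |
| 516.6*, J84.841, J84.842, J84.843, J84.848 | ILD of childhood |
| J84.83 | surfactant mutations |

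- Adult ICD-10 codes checked: J84.10, J84.111 to J84.117, J84.17, J84.89 and J84.9, which makes 11. Captured: J84.115 only, so 1 of 11.
- ICD-9 codes checked: 515, 516.30 to 516.37, 516.8 and 516.9, which makes 11. Captured: 516.34 only, so 1 of 11.
- Among those missed are unspecified pulmonary fibrosis (J84.10), idiopathic pulmonary fibrosis (J84.112) and unspecified ILD (J84.9).

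These are counts of codes, not of patients. Because both ICD versions are affected, the gap covers the whole entry window.

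**Lung cancer**

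- The C34 family has 16 codes: three each under C34.0, C34.1, C34.3, C34.8 and C34.9 (unspecified, right, left), plus C34.2. That is 5 × 3 + 1 = 16.
- The annex lists 6: C34.00, C34.10, C34.2, C34.30, C34.80 and C34.90.
- The other 16 − 6 = 10 are the right- and left-side codes. None is matched, whether codes are read exactly or as prefixes.
- C46.5, C78.0 and D02.2 show the same pattern: only C46.50, C78.00 and D02.20 are listed.

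The annex uses wildcards or side variants where it wants them. The cancer covariate is C00%-C76%, the ILD row itself has 516.6*, and the basal cell list gives C44.611, C44.612 and C44.619. A wildcard on C34 therefore cannot be assumed. As printed, a patient coded only C34.11 is a cancer comorbidity case but not a lung cancer exclusion.

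**Part of the window affected by the lung cancer gap**

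- Entry window, January 2013 to March 2019: 6 × 12 + 3 = 75 months.
- ICD-10 period, October 2015 to March 2019: 3 + 36 + 3 = 42 months.
- 42 / 75 = 56%. The lung cancer exclusion is weaker for later entrants.

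**Number retained**

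This cannot be calculated. The documents give no prevalence of either condition, and the attrition table in section 7.7 has no row for criterion 2.

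**The case against.** A reader might infer that lung cancer patients in general stay in the cohort. The documents do not support that. The criterion looks at all history before the index date, and section 7.5 says data reach back to January 2006. A single pre-index diagnosis with any listed ICD-9 code, an unspecified-side code, C34.2 or Z85.118 removes the patient. Only those whose whole history carries right- or left-side codes alone remain. The ICD-9 part assumes that 162 is read as a category. The lung transplant list is not affected.

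A reader might also infer a broad distortion of the primary outcome in a known direction. That is not supported either. A severe exacerbation needs a principal discharge diagnosis of COPD, and the emergency department component needs a COPD diagnosis, so a respiratory admission alone is not an event. The exposed routes are the same-day dispensing rule and the pneumonia outcome. The paragraph following the outcome list in section 7.4.2.1 ties dispensing to an emergency department visit for COPD; if that wording governs, the first route narrows. Retained patients enter both arms. Lung cancer enters the propensity score through the cancer covariate, and the high-dimensional step may pick up ILD.

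Three further points are fair. The ILD reading depends on ICD descriptors that the annex does not print. The annex is loosely written in places (bare categories, repeated codes), so exact matching is an inference. Loss of table rows in the text version cannot be fully ruled out, although neighbouring rows look intact.

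These points narrow the consequence, but the mismatch stands. No reading of the printed ILD row brings in 515, J84.10, J84.112 or J84.9. Adjustment, where it occurs, neither enforces a stated exclusion nor restores outcome specificity.

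**Conclusion.** Annex 3.3 does not implement exclusion criterion 2. For adult ILD the criterion is close to inoperative: in a cohort aged 40 or older the row works for one subtype, with 1 of 11 adult codes captured in each ICD version. For lung cancer the defect is partial: 0 of 10 sided C34 codes are captured, it applies to the ICD-10 period (42 of 75 entry months), and it concerns only patients with no listed code anywhere in their history.

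The conclusion rests on the standard ICD meanings of the codes and on the annex being programmed as printed. It does not extend to a number of patients, a percentage of either arm or a direction of bias. Any such figure would need prevalences that the documents do not contain, and the counts of 5,469 and 42,227 in section 7.7 are taken at the COPD diagnosis step, with no row for criterion 2. The correction is still warranted, because a stated eligibility rule does not work as coded and repairing it is cheap.

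**What to change.** Make the annex match criterion 2:

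- **ILD:** replace the row with code families that cover adult disease in both ICD versions, such as ICD-9 515 and the adult 516.x codes, and ICD-10 J84.x.
- **Lung cancer:** use side-inclusive families (C34.%, C46.5%, C78.0%, D02.2%), keep the other listed codes, and state that ICD-9 162 means the whole category.
- **Extraction and reporting:** re-run the cohort extraction and add rows to the attrition table showing the number excluded for each condition in each arm.

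The cost is a code-list edit and a re-run on existing data. The cohort becomes slightly smaller. Broad codes such as 515 or J84.10 may also remove some patients with non-specific fibrosis. Section 7.3 does not define how wide ILD should be, so the chosen breadth should be stated with its reason.
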